4.3 Sample Size

For Substudy 1 (Phase 2b portion of the study), a total of 250 subjects will be equally allocated to four treatment groups and the placebo group, representing a randomization ratio of 1:1:1:1:1. The sample size for this study is based on the expected proportion of subjects who achieve clinical remission per Adapted Mayo score at Week 8. Assuming

clinical remission rate of 12% in the placebo arm and maximum of 30% in at least one of the ABT-494 QD treatment arms at Week 8, a sample size of 50 subjects per treatment group is sufficient to test for the presence of a dose response signal, to select the best dose response model for the observed data out of a pre-specified set of candidate models, and to estimate target doses of interest (e.g., the minimum effective dose, MED) via modeling using MCP-Mod (Multiple comparison procedure and modeling) approach. This approach provides an average power of 68% to detect a dose effect at 5% level of significance (two-sided) with the log linear, E_{\max} , exponential, logistic and $\text{sig}E_{\max}$ models pre-specified as likely candidates to characterize the dose-response for ABT-494 for the primary endpoint of clinical remission per Adapted Mayo score.

4.4 Substudy 1 Double-Blind Analysis

An analysis of the double-blind portion of Substudy 1 for primary endpoint and secondary efficacy variables as well as safety data collected from Baseline through double-blind Week 8 will be performed after the last subject in the ITT1A population (Section 5.1 for definition) completes the 8-week double-blind Substudy 1. A database lock will be performed and any discrepant data will be clarified before the lock.

4.5 Derived, Defined and Transformed Variables

The following defined variables will be used:

- Full Mayo Score
 - Full Mayo Score is defined as the composite score of UC disease activity based on the subscores of stool frequency (0 – 3), rectal bleeding (0 – 3), physician's global assessment (0 – 3) and endoscopy (0 – 3). This score ranges from 0 – 12 points with higher scores representing more severe disease (also see Section 6.0 for the rules for calculation of rectal bleeding and stool frequency subscores). A description of the Mayo Scoring System can be found in Appendix H of the protocol.
 - Clinical Response per Full Mayo Score is defined as a decrease in Full Mayo Score of ≥ 3 points and $\geq 30\%$ from Baseline, PLUS a decrease in the rectal bleeding subscore [RBS] ≥ 1 or an absolute RBS of 0 or 1.

- Clinical Remission per Full Mayo Score is defined as Full Mayo Score ≤ 2 with no subscore > 1 .
- Partial Mayo Score
 - Partial Mayo Score is defined as the composite score of UC disease activity based on the subscores of stool frequency, rectal bleeding, and physician's global assessment and DOES NOT include the endoscopy subscore. This score ranges from 0 – 9 points (also see Section 6.0 for the rules for calculation of rectal bleeding and stool frequency subscores).
 - Response per Partial Mayo Score is defined as a decrease in Partial Mayo Score ≥ 2 points and $\geq 30\%$ from Baseline, PLUS a decrease in RBS ≥ 1 or an absolute RBS of 0 or 1.
 - Remission per Partial Mayo Score is defined as Partial Mayo Score ≤ 2 , with no subscore > 1 .
- Adapted Mayo Score
 - Adapted Mayo Score is defined as Full Mayo Score minus the Physician's Global Assessment (PGA) subscore. This score ranges from 0 – 9 points.
 - Remission per Adapted Mayo Score is defined as an Adapted Mayo Score ≤ 2 , with stool frequency subscore ≤ 1 , RBS of 0, and endoscopic subscore ≤ 1 .
 - Response per Adapted Mayo Score is defined as a decrease in the Adapted Mayo Score ≥ 2 points and $\geq 30\%$ from baseline, PLUS a decrease in RBS ≥ 1 or an absolute RBS ≤ 1 .
- Endoscopic Remission: Endoscopic subscore of 0
- Endoscopic Improvement: endoscopy subscore of 0 or 1

5.0 Analysis Populations

5.1 Definition for Analysis Populations

The following populations will be used for analyses in Substudy 1:

The intent-to-treat (ITT) analysis set for Substudy 1 includes all randomized subjects who received at least one dose of study drug from Substudy 1 at the time of dose-selection

analysis, denoted as ITT1A. The ITT analysis set that includes all ITT1A subjects, plus all the additional subjects who were randomized to ABT-494 30 mg and 45 mg groups during the dose-selection analysis period is denoted as ITT1B.

The safety analysis set in Substudy 1 consists of all subjects who received at least one dose of study medication in the study. For the safety analysis sets, subjects are assigned to a treatment group based on the treatment actually received, regardless the treatment randomized. Safety analyses of Substudy 1 will be carried out using the safety analysis set.

5.2 Variables Used for Stratification of Randomization

In Substudy 1 (Phase 2b 8 week induction), 250 subjects who meet all the inclusion and none of the exclusion criteria defined in the protocol (Section 5.2.1 and Section 5.2.2) will be centrally randomized in a 1:1:1:1:1 ratio to receive one of five treatment groups at Baseline (Week 0) in a double-blind manner (ABT-494 7.5 mg QD, 15 mg QD, 30 mg QD, 45 mg QD, or placebo QD). Randomization will be stratified by previous biologic use, baseline corticosteroid use and baseline Adapted Mayo score (≤ 7 and > 7).

6.0 Analysis Conventions

Definition of Baseline

The Baseline visit date for Substudy 1 is the date when the first dose of study drug is received and referred to as Day 1 or Week 0. The Baseline value for a variable is defined as the last non-missing value on or before the date of the first dose of study drug.

Definition of Final Observation

Final Observation in the 8-week Substudy 1 is defined as the last non missing observation collected within 30 days following the last dose of study drug for subjects who are not re-randomized into Substudy 3 or enrolled into Study M14-533, and on or before the day of the first dose of study drug in Substudy 3 or Study M14-533 for subjects who are re-randomized into Substudy 3 or enrolled into Study M14-533. Of note, the efficacy,

laboratory, and vital sign evaluations performed on the day of the first dose of study drug in Substudy 3 or Study M14-533 for Substudy 1 subjects will be included in the efficacy and safety analyses for Substudy 1. AEs with onset on the date of the first dose of Substudy 3 or Study M14-533 will be attributed to Substudy 3 or Study M14-533, respectively.

Definition of Study Drug Exposure

Study drug exposure during Substudy 1 is measured as follows:

Study drug exposure = (date of last dose of study drug – date of first dose of study drug + 1 day).

Definition of Rx Days (Days Relative to the First Dose of Study Drug)

Rx Days are calculated for each time point of interest and it provides a quantitative measure of days between the event and the first dose date. That is, the Rx Day is calculated as the event date minus the date of first dose of study drug plus 1. The Rx Day will be a negative value when the time point of interest is prior to the date of first dose of study drug, and the Rx Day will be a positive value when the time point of interest is after the first dose date. By this calculation algorithm the first dose day is Rx Day 1, while the day prior to the date of first dose is defined as Rx Day –1 (there is no Rx Day 0). Rx Days are used to map actual study visits to the protocol specified study visits.

Definition of Analysis Windows

Since subjects do not always adhere to the study visit schedule, the following rules will be applied to assign actual visits to protocol-specified visits including early termination visits. For each study visit mentioned in the protocol, a nominal or target day will be selected to represent the corresponding visit along with a window around the target day. Windows will be selected in a non-overlapping fashion so that a date collected on the CRF does not correspond to multiple visit windows. Moreover, windows will not discard any Post-Baseline measurement recorded on the CRF. If a subject had two or more actual visits in one visit window, the visit closest to the schedule visit will be used as the study

visit for that window. If two visits are equidistant from the target, then the later visit will be used for reporting. If more than one assessment is collected on the same day, then the average of those assessments will be used in analyses.

Table 1. Visit Windows for Analysis of Partial Mayo Score, HCRU, Laboratory Parameters and Vital Signs for Substudy 1

Scheduled Week	Nominal Day	Time Window (Rx Day Range)
Week 0	1 ^a	≤ 1
Week 2	15	2 – 22
Week 4	29	23 – 36
Week 6	43	37 – 50
Week 8	57	51 – 71 ^b

Rx Day A = date of visit – date of first study drug in Substudy 1 + 1.

- a. Day of first dose of study drug in Substudy 1.
- b. Rx Day 71 or the date of the first dose of Substudy 3/Study M14-533, whichever is earlier.

Table 2. Visit Windows for Analysis of Mayo Score, ECG, Fasting Lipids and Lymphocyte Subset for Substudy 1

Scheduled Week	Nominal Day	Time Window (Rx Day Range)
Week 0	1 ^a	≤ 1
Week 8	57	2 – 71 ^b

Rx Day = date of visit – date of first study drug in Substudy 1 + 1.

- a. Day of first dose of study drug in Substudy 1.
- b. Rx Day 71 or the date of the first dose of Substudy 3/Study M14-533, whichever earlier.

Table 3. Visit Windows for Analysis of hs-CRP and Patient Questionnaires (IBDQ, SF-36, etc.) for Substudy 1

Scheduled Week	Nominal Day	Time Window (Rx Day Range)
Week 0	1 ^a	≤ 1
Week 2	15	2 – 22
Week 4	29	23 – 43
Week 8	57	44 – 71 ^b

Rx Day = date of visit – date of first study drug in Substudy 1 + 1.

- a. Day of first dose of study drug in Substudy 1.
- b. Rx Day 71 or the date of the first dose of Substudy 3/Study M14-533, whichever earlier.

Table 4. Visit Windows for Analysis of Fecal Calprotectin for Substudy 1

Scheduled Week	Nominal Day	Time Window (Rx Day Range)
Week 0	1 ^a	≤ 1
Week 2	15	2 – 36
Week 8	57	37 – 71 ^b

Rx Day = date of visit – date of first study drug in Substudy 1 + 1.

- a. Day of first dose of study drug in Substudy 1.
- b. Rx Day 71 or the date of the first dose of Substudy 3/Study M14-533, whichever earlier.

Rules for Efficacy Assessment Based on Concomitant Treatment

Subjects in whom the maximum steroid dose exceeds the dose used at Baseline will be considered non-responders and will be censored for efficacy assessments (i.e., they will be considered non-responders for categorical endpoints and will have Baseline values carried forward for non-categorical assessments) from that point forward through the end of the study. These subjects will continue to be evaluated in the safety analysis set.

The equivalent steroid dose will be determined based on [Table 5](#):

Table 5. Equivalent Steroid Dose

Corticosteroid	Equivalent Dose (mg)
Cortisone	25
Hydrocortisone	20
Prednisone	5
Prednisolone	5
Triamcinolone	4.0
Methylprednisolone	4.0
Betamethasone	0.75
Dexamethasone	0.75
Budesonide	1
Beclomethasone	5

Subjects in whom the following UC-related medications (oral aminosalicylates, systemic corticosteroids, and MTX) that were not being taken at Baseline and are initiated during

the study or who have dosages of these medications increased to greater than the dose taken at Baseline will be censored for efficacy assessments (i.e., will be considered non-responders for categorical endpoints and will have the last values carried forward for non-categorical assessments) from that point through the end of the study. These subjects will continue to be evaluated in the safety analysis set.

Definition of Missing Data Imputation

The following imputation methods will be used to impute missing values in the efficacy analyses. In addition, an observed case analysis will be performed.

Non-Responder Imputation (NRI)

The NRI approach is used for binary efficacy variables. These variables can take values of 'Achieved' or 'Not Achieved' or may be missing for any reason including discontinuation from study. According to the NRI imputation approach, all missing values will be considered as 'Not Achieved.'

Last Observation Carried Forward (LOCF)

For all variables (categorical variables and continuous variables), the following rules will be used for the LOCF approach:

1. Baseline and Pre-Baseline values will not be used to impute the missing Post-Baseline values.
2. Missing values after Study Day 1 will be imputed using the latest non-missing values after Day 1 and prior to the missing value. If there are no non-missing values after Baseline, then the LOCF value will be missing.

Hybrid Multiple Imputation Method

Primary endpoint of clinical remission will be analyzed using hybrid multiple imputation method. Subjects who discontinue prior to Week 8 due to lack of efficacy or AEs will be

considered as "not achieved" for clinical remission. Subjects who discontinue for other reasons will be categorized according to multiple imputations.

Mixed-Effect Model Repeated Measure (MMRM)

The MMRM model will be used for continuous efficacy variables with longitudinal data as the primary analysis. The MMRM model includes the baseline values as covariate; randomization stratification factors, treatment, time point and treatment-by-time point interaction as fixed effects; and subjects within treatment as random effect. An unstructured (co)variance structure will be used to model the within subject error. The comparison at a time point will be the contrast between treatments at that time point. Satterthwaite's approximation will be used to estimate denominator degrees of freedom.

Observed Case (OC)

Observed case analysis will be performed such that missing values will not be imputed.

Imputation of Missing Dates

For Baseline, efficacy, and safety parameters, if the day and/or month are missing, the following conventions will be used to impute the missing dates:

- 01 for missing start day
- End of month for missing end day
- January 1st for missing start month
- December 31st for missing end month

In case of partially missing AE start and stop dates, the dates will be imputed by comparing to first dose date of study medication so that the corresponding AEs will be made treatment-emergent whenever possible. If the start date of an AE is partially missing and the month is the same as the start date of a new therapy, the AE will be made treatment emergent to the new therapy.

In case of missing or partially missing study drug dosing dates, the dates will not be imputed. Subjects will be treated as not receiving dose on that date.

Rules for Calculation of Stool Frequency Subscore and Rectal Bleeding Subscore

The diary entries on the days the subjects take endoscopy preparation medications, the day of endoscopy procedure, and 2 days after endoscopy procedure will be excluded. If a subject takes an antidiarrheal on a day, the stool frequency subscore is considered as 3 for that day. For the calculation of the stool frequency subscore and the rectal bleeding subscore at each visit, the most recent consecutive 3-day period prior to the study visit will be used.

If diary entries from the 3 consecutive days prior to the visit are not available, the average of the entries from the most recent 3 non-consecutive days will be utilized. If less than 3 days of diary data are available, stool frequency and rectal bleeding subscores will be considered missing.

Rounding to one decimal place will be applied to the calculation above for the subscores, Adapted Mayo Score, Partial Mayo Score and Full Mayo Score.

The last day of the days used for stool frequency and rectal bleeding subscore calculation will be used to decide the actual visits that should be assigned to the Mayo Score and Partial Mayo Score data.

Definition of Prior Medications

Prior medications include all medications with an end date before the first study drug dose date, and the medications with start date prior to the first dose date but end date missing.

Definition of Medication Use at Baseline

Medications are considered to be used at Baseline if the medication start date is on or before the first study drug dose date and the medication end date is on or after the

first dose date. All medications with a start date after the first dose date or an end date before the first dose date are excluded.

Definition of Concomitant Medications

Concomitant medications include medications with a start date prior to the Baseline date which are continuing after Baseline and all medications with a start date between the Baseline date and last study drug administration + 1 day. All medications with an end date prior to the first dose date are excluded.

If the start date is completely missing for a medication and if the stop date is before the baseline date, it is considered previous medication and not further evaluated. In addition to start date being completely missing, if the stop date is also completely missing or the stop date is on or after the baseline date, it will also be considered as a concomitant medication.

7.0 Demographics, Baseline Characteristics, Medical History, and Previous/Concomitant Medications

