Subjects in whom UC-related corticosteroids are initiated (not taken at Baseline) or who have dosages of these medications increased to greater than the dose taken at Baseline during Substudy 1 or Study 2, or UC-related rescue medications are used during Substudy 3 will be considered a failure for categorical efficacy endpoints, and for non-categorical assessments will have the last values carried forward from that time point

through the end of the substudy for Substudy 1 and will be handled by MMRM for Substudy 2 and Substudy 3.

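### The Substudy 1 SAP sets two incompatible carry-forward rules for continuous endpoints after a systemic corticosteroid start or increase above Baseline

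*SAP*

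**What the plan says.** Both rules stand in Section 6.0 of the Substudy 1 SAP, under the heading on efficacy assessment and concomitant treatment.

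- First rule. The trigger is any steroid dose above Baseline, with equivalent doses taken from Table 5: "Subjects in whom the maximum steroid dose exceeds the dose used at Baseline will be considered non-responders". For continuous endpoints these subjects "will have Baseline values carried forward for non-categorical assessments".
- Second rule. The trigger is a start or an increase of listed drugs: "Subjects in whom the following UC-related medications (oral aminosalicylates, systemic corticosteroids, and MTX) that were not being taken at Baseline", or subjects "who have dosages of these medications increased to greater than the dose taken at Baseline will be censored for efficacy assessments". For continuous endpoints these subjects "will have the last values carried forward for non-categorical assessments".

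Both rules apply from the event to the end of the study, and both make the subject a non-responder for categorical endpoints.

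The same section's LOCF definition states that "Baseline and Pre-Baseline values will not be used to impute the missing Post-Baseline values", and that the LOCF value is missing if nothing was observed after Baseline. Section 10.3 makes LOCF the primary approach for continuous endpoints analysed by ANCOVA.

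Protocol Section 8.1.3 gives one rule for a UC-related corticosteroid start or increase in Substudy 1: "for non-categorical assessments will have the last values carried forward from that time point".

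**The concern.** A systemic corticosteroid raised above its Baseline dose meets both triggers. So does a new start, since any dose exceeds a Baseline dose of zero. The SAP does not rank the two rules and does not exempt steroids from the second, so a programmer cannot satisfy both.

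Carrying Baseline forward removes any improvement seen before the event; carrying the last value forward keeps it. If the analyst chooses without a written rule, the results for these subjects cannot be reproduced from the SAP, and the choice may look as if it was made after the data were seen.

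**Working it through.** The plan states no figure on this point, so the check is mainly a comparison of texts.

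**Step 1: where the triggers overlap.**

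| Event | First rule | Second rule |
|---|---|---|
| Systemic corticosteroid started or raised above Baseline | applies | applies |
| Steroid increase not classed as systemic | applies | does not apply |
| Oral aminosalicylate or MTX started or raised | does not apply | applies |

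The conflict is confined to the first row.

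**Step 2: which endpoints differ.** For categorical endpoints both rules give non-response. The primary endpoint (clinical remission at Week 8) is binary. Of the seven ranked secondaries in Section 10.3, only number 5, change in Full Mayo score, is continuous; 7 - 1 = 6 are binary. The conflict therefore reaches one ranked endpoint and the non-ranked continuous measures.

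**Step 3: repeated measures.** Tables 1 and 3 of the SAP give post-baseline windows at Weeks 2, 4, 6 and 8 for Partial Mayo, and at Weeks 2, 4 and 8 for hs-CRP and questionnaires. Let B be the Baseline value and L the last post-baseline value before the event.

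- First rule: imputed change = B - B = 0.
- Second rule: imputed change = L - B.
- Gap between the rules = L - B.

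Assumed example: Partial Mayo is 6 at Baseline and 3 at Week 4, and a systemic steroid is raised above Baseline at Week 5. The Week 8 change is 6 - 6 = 0 under the first rule and 3 - 6 = -3 under the second.

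For scale, ITT1A was planned at 50 subjects per arm. One such subject moves the unadjusted arm mean by (L - B)/50. If the prior improvement is assumed to lie between 1 and 3 points, that is 1/50 = 0.02 to 3/50 = 0.06 points per subject. The number of such subjects in each arm is not in the documents, so no effect on a treatment difference follows.

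**Step 4: ranked secondary 5.** Table 2 gives the Mayo score only two windows: Week 0, and one post-baseline window (Rx Days 2 to 71) assigned to Week 8. A subject whose steroid is raised before the Week 8 assessment usually has no earlier post-baseline Full Mayo value.

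- First rule: Baseline is carried forward, so the change is 0 and the subject stays in the ANCOVA.
- Second rule with the LOCF definition: there is nothing to carry, so the value is missing and the subject drops out.
- Second rule read literally, with Baseline as the last value: the change is 0, the same as the first rule. The LOCF definition rules this reading out for LOCF, and the SAP does not say that it applies here.

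**Step 5: protocol and dates.** Protocol 8.1.3 agrees with the second rule. Protocol Appendix K lists that paragraph as new in the current amendment, whereas the Substudy 1 SAP was written for Amendment 2 of 10 October 2017. The mismatch with the current protocol can therefore be explained by timing. The conflict inside the SAP cannot.

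**The case against.** The strongest reply is that the consequence is small. The primary endpoint and six of the seven ranked secondaries do not depend on the choice. Protocol Section 5.2.3 asks for stable UC medication in Substudies 1 and 2 and prohibits starting rectal or systemic corticosteroids during induction, so the event should be uncommon. Substudy 1 is a Phase 2b dose-ranging study tested at nominal levels without multiplicity adjustment (SAP Section 10.4), and Protocol Section 5.6.1 keeps its data out of Phase 3 inference. The dose-selection analysis is done and the 45 mg dose chosen. All of this stands and limits the weight of the point. It does not tell anyone which rule to apply.

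A reader might infer more: that every continuous endpoint is affected, and that the Full Mayo treatment difference shifts by a calculable number of points because placebo subjects escalate more often. The documents do not support this. Only subjects with the event are affected. Full Mayo normally has no intermediate value to carry, so the choice there is between a change of 0 and a missing value, not between 0 and a partial improvement. More frequent escalation on placebo is plausible, but no rate by arm is given. Nor can the SAP be faulted for departing from a protocol paragraph that was added after it was written.

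**Conclusion.** The contradiction is real and can be read directly from Section 6.0: one event, two imputed values, no precedence. It concerns continuous endpoints only, and only subjects who start or raise a systemic corticosteroid above Baseline. Repeated measures can differ by the whole improvement seen before the event. Ranked secondary 5 usually differs in whether the subject is included with a change of 0 or excluded. That second conclusion rests on reading the last-value rule together with the SAP's own LOCF definition; on the literal reading the two rules coincide for that endpoint. The overall effect depends on event counts that the documents do not give and may be small. The point is still worth correcting, because Section 10.1 repeats the ranked secondary analyses in ITT1B for the final clinical study report, and that report must be able to state which rule was used.

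**What to change.** Keep the first rule's trigger, its non-responder handling and Table 5. Change only its clause on continuous endpoints from Baseline to last value, so that it agrees with the second rule and with Protocol 8.1.3. Do not delete the whole sentence. The second rule names only systemic corticosteroids, so deletion would remove the SAP's non-responder rule for steroid increases not classed as systemic and leave Table 5 without a purpose. That would reach the primary endpoint, which the present conflict does not.

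Add one line saying what is done when no post-baseline value precedes the event; this settles ranked secondary 5. Because the dose-selection analysis has already been run, state in the study report which rule was applied to ITT1A, use the corrected rule for ITT1B, and show the other rule only as a labelled sensitivity analysis.

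The cost is one clause, one clarifying line, a sentence in the report and one optional rerun.
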